3.0 Inclusion/Exclusion criteria

- Inclusion Criteria
 - Age of 18 years or older
 - Randomized within 24 hours of presentation during a hospital admission for hypervolemic decompensated heart failure defined as either:
 - pulmonary artery catheterization with a pulmonary capillary wedge pressure greater than 19mmHg plus a systemic physical exam finding of hypervolemia (peripheral edema, ascites, or rales on auscultation)
 - in the absence of pulmonary artery catheterization data 2 of the following signs or symptoms: peripheral edema, ascites, jugular venous pressure > 10mmHg, orthopnea, paroxysmal nocturnal dyspnea, 5-pound weight gain, or signs of congestion on chest x-ray or lung ultrasound

- Standard-of-care monitoring on an inpatient ward and standard-of-care basic metabolic panel laboratory assessment once daily during the study period
- Planned or current use of IV loop diuretic therapy during current hospitalization
- eGFR \geq 25 ml/min/1.73m² by the MDRD equation
- Exclusion Criteria
 - Type 1 diabetes
 - Serum glucose < 80mg/dl at enrollment
 - Systolic blood pressure < 90mmHg at enrollment
 - Requirement of intravenous inotropic therapy at enrollment or anticipated need of therapy during the study period
 - History of hypersensitivity to any SGLT2 inhibitors
 - Women who are pregnant or breastfeeding
 - Severe anemia (Hemoglobin < 7.5g/dl)
 - Severe uncorrected aortic or mitral stenosis
 - Inability to perform standing weights or measure urine output accurately
 - History of diabetic ketoacidosis
 - Chronic combination nephron blockade with loop and thiazide therapy as an outpatient scheduled daily for more than 7 days prior to admission (Does not include HCTZ < 50mg for blood pressure)
 - Diffuse anasarca with 4+ edema and projected hypervolemia exceeding 40-pounds
 - Severe hepatic impairment (Child-Pugh class C if hepatic impairment is in question)
 - Clinical picture consistent with acute myocardial infarction including troponin rise and fall or ischemic changes on electrocardiogram
 - Site investigator determines the subject is not a good candidate to participate in study at this time

4.0 Patient screening, consent, and randomization

We will perform a randomized, open-label, multicenter trial to investigate the safety and clinical effects of initiating dapagliflozin vs standard of care in patients admitted to the hospital with ADHF with protocolized diuretic therapy in both treatment arms.

4.1 Screening

To identify candidates, we will collaborate with our Emergency Department. We are able to screen, consent, and randomized study candidates in the Emergency Department. Additionally, patients with ADHF will be screened on the HF team daily by a member of

the HF team. Finally, we will utilize an electronic HF dashboard embedded within the electronic medical record to identify candidates across the medical center by their International Classification Disease code history, natriuretic peptide concentration adjusted for body-mass index, and use of intravenous loop diuretic therapy.

We will utilize up to 5 additional sites for enrollment including but not limited to:

- [name] St Thomas Hospital System in Nashville, TN
- [name] Centennial Hospital in Nashville, TN
- [name] University of Mississippi in Jackson, MS
- [name] Integris Baptist Medical Center
- [name] Univeristy of North Carolina

4.2 Consent

The study will be reviewed with the prospective participant (surrogate) by the investigator or study personnel. The prospective study participant (surrogate) will be given adequate time to read the written consent form. The investigator or study personnel will be available to answer questions about the study including procedures, risks, and alternatives. The informed consent form will be signed and dated by the patient or legally authorized representative as per local regulation.

The consent will allow for protected health information (PHI) to be transferred to REDCap to be analyzed by the Biostatistical team. All privacy regulations will be followed (i.e., Health Insurance Portability and Accountability Act [HIPAA]).

4.3 Randomization

Randomization will occur during the hospitalization within 24 hours of evaluation of AHF. Enrollment and randomization will be accomplished by study personnel logging into REDCap, confirming the inclusion and exclusion criteria have been satisfied, and using the REDCap randomization engine. Participants will then be randomized to either dapagliflozin or standard-of-care and will be registered as *randomized*.

[figure not shown]
5.0 Study Procedures

All patients will receive a low sodium diet (2g/day) with a 2000ml fluid restriction. Patients will receive standard-of-care laboratory monitoring (including at minimum once daily basic metabolic panel and baseline complete metabolic panel), vital sign monitoring, and strict urine output monitoring/quantification.

5.1 Diabetic Therapies for patients with a diagnosis of Type 2 diabetes

After enrollment, all previous diabetic therapies will be discontinued. Patients will be randomzed in a 1:1 ratio to standard of care with protocolized diuretic therapy or standard of care with protocolized diuretic therapy plus the addition of open label SGLT2 inhibitor therapy with dapagliflozin 10 mg orally once daily for the duration of the study, which will be until 5 days or hospital discharge. The patient will receive standard

of care point of care blood glucose monitoring 4 times daily (before meals and at bedtime) and correctional insulin according to a blood glucose scale. For patients requiring large doses of basal insulin, the patient will be continued on a reduced dose of basal insulin. Insulin initiation and titration algorithms are in Appendix B.

Non-insulin hypoglycemic: chronic, outpatient oral hypoglycemic medications which may include but are not limited to sulfonylureas, DPP-4 inhibitors, and/or metformin.

5.2 Heart Failure Therapies

The titration of non-diuretic heart failure therapies will be left to the direction of the treating physician.

5.3 Diuretic Therapies

5.3.1 Initial loop diuretic regimen

If the patient has received loop diuretic dose(s) prior to randomization, proceed to Section 5.3.2 and titrate the current loop diuretic regimen according to diuretic protocol provided.

If the patient's first IV loop diuretic dose is after enrollment, the initial loop diuretic regimen after enrollment will be as follows:

Loop diuretic naïve: If the patient does not take a scheduled loop diuretic as an outpatient, the initial IV loop diuretic dose will be 40mg of furosemide equivalents every 12 hours. (1mg IV bumetanide = 40mg IV furosemide)

Chronic, oral loop diuretic therapy: If the patient takes a scheduled loop diuretic regimen as an outpatient prior to hospital admission, the initial IV loop diuretic daily dose will be 2 to 2.5 times the total daily home regimen dose. The calculated daily dose will be given as 50% the total daily dose as an IV bolus dose every 12 hours. Individual bolus doses exceeding 200mg IV furosemide equivalents will be capped to 200mg IV furosemide equivalents, so that the highest initial regimen will be 200mg IV every 12 hours.

Diuretic conversion: 80mg oral furosemide = 40mg IV furosemide = 20mg oral torsemide = 1mg oral/IV bumetanide

5.3.2 Loop diuretic titration

Diuretic therapy can be titrated every 12 - 24 hours. Diuretic titration recommendations will be provided per the table below to first maximize IV loop diuretic therapy before addition of combination nephron blockade to limit non-loop diuretic therapy impact.

Goal urine output		Suggested Diuretic Regimen Titration
Over 12 h Over 24 h		
< 1.5 liters	< 3 liters	Move down diuretic grid 1 row to increase diuretic intensity
1.5 – 2.5 liters	3-5 liters	Continue on same diuretic regimen
> 2.5 liters	> 5 liters	Move up diuretic grid 1 row to decrease diuretic intensity

Current IV Diuretic Regimen	Suggested New IV Diuretic Regimen		
(Furosemide IV Equivalent mg/day)	(Furosemide IV Equivalent in mg)		
≤ 80 mg /day	160mg daily: 80mg IV Q12H		
81-200mg/day	320mg daily: 160mg IV Q12H		
201-320mg/day	480mg daily: 240mg IV Q12H or 20mg/h infusion*		
321-480mg/day	600mg daily: 300mg IV Q12H or 25mg/h infusion*		
481-600mg/day	720mg daily: 30mg/h infusion*		
601-720mg/day	960mg daily: 40mg/h infusion*		
721-960mg/day	1,440mg daily: 60mg/h infusion* + metolazone 5 mg daily		
>960mg/day	1,920mg daily: 80mg/h infusion* + metolazone 10 mg daily		

*Continuous IV infusions will be preceded by a 80mg IV furosemide loading dose unless a bolus dose was given in the previous 2 hours.

Non-study diuretic therapies

Use of non-study diuretic therapies including: spironolactone doses \geq 100mg/day, eplerenone \geq 100mg/day, non-study thiazides (metolazone or HCTZ> 12.5mg or other thiazide), non-study loop diuretics, systemic acetazolamide, triamterene, or amiloride therapy is discouraged and considered a protocol deviation.

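### The one-row titration instruction in protocol section 5.3.2 contradicts the grid it points to: read literally, the decrease leaves seven of eight regimens unchanged, and no reading covers every dose

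*Protocol*

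**What the plan says.** Protocol section 5.3.2 has two tables. The instruction table sets the action by urine output:

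- below 1.5 L in 12 h or 3 L in 24 h: "Move down diuretic grid 1 row to increase diuretic intensity"
- within the goal range: "Continue on same diuretic regimen"
- above 2.5 L in 12 h or 5 L in 24 h: "Move up diuretic grid 1 row to decrease diuretic intensity"

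The grid has a left column headed "Current IV Diuretic Regimen", given as mg/day bands, and a right column headed "Suggested New IV Diuretic Regimen". Its first row pairs 80 mg/day or less with "160mg daily: 80mg IV Q12H", and its second pairs 81-200 mg/day with "320mg daily: 160mg IV Q12H". The text presents the grid as recommendations.

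Section 5.3.1 sets the doses that enter the grid. For a loop-naive patient first dosed after enrollment, "the initial IV loop diuretic dose will be 40mg of furosemide equivalents every 12 hours", which is 80 mg/day. A patient on chronic oral therapy starts at 2 to 2.5 times the home daily dose, with each bolus capped at 200 mg, so at most 400 mg/day. A patient already given a loop diuretic before randomization goes straight to section 5.3.2 on the current regimen.

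Section 2.1 divides weight change by all loop diuretic administered. Section 10.0 and the SAP (Power and Sample Size) assume an SD of 0.25 kg/40 mg, on the expectation that the diuretic protocol will narrow variation in loop dosing.

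**The concern.** In rows 1 to 7 the right-hand regimen is already higher than the whole band on its left, and it falls in the next row's band. Reading straight across is therefore an increase in itself. The instruction adds a one-row move without saying which column locates the patient, or whether reading across already counts as that move. An instruction labelled as a decrease can then return the same or a higher dose.

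Three parts of the plan rest on this table:

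- the denominator of the primary endpoint;
- the argument for an SD of 0.25, well below the 0.47 kg/40 mg that section 10.0 reports at the sponsor's own center;
- the worsening-heart-failure endpoint, one component of which counts escalations. The protocol summary, section 2.2 and the SAP (Secondary Endpoints) count grid rows (2 rows). Section 5.4 counts increases (2 or more).

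**Working it through.** **Inputs (section 5.3.2).** Current-dose bands by row, in mg/day: up to 80, 81-200, 201-320, 321-480, 481-600, 601-720, 721-960, above 960. New regimens by row: 160, 320, 480, 600, 720, 960, 1,440, 1,920.

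**Step-down under three readings.** Literal: find the row by current dose, go up one row, read the new regimen. Regimen column: find the dose in the right column and go up one. Dose column: find the band in the left column and go up one.

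| Current mg/day | Literal | Regimen column | Dose column |
|---|---|---|---|
| 160 | 160 | no row above | up to 80 |
| 320 | 320 | 160 | 81-200 |
| 480 | 480 | 320 | 201-320 |
| 600 | 600 | 480 | 321-480 |
| 720 | 720 | 600 | 481-600 |
| 960 | 960 | 720 | 601-720 |
| 1,440 | 1,440 | 960 | 721-960 |
| 1,920 | 1,440 | 1,440 | 721-960 |
| 80 | no row above | not listed | no row above |
| 100 | 160 | not listed | up to 80 |
| 200 | 160 | not listed | up to 80 |
| 240 | 320 | not listed | 81-200 |
| 400 | 480 | not listed | 201-320 |

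Read literally, seven of the eight grid regimens do not change. Among starting doses up to the 400 mg cap, 81-159 rises to 160, 201-319 rises to 320, and 321-400 rises to 480. Doses of 161-200 fall to 160, and 160 and 320 do not change. The regimen column lowers seven of the eight regimens but has no entry for 80, 100, 200, 240 or 400 and no row above 160. The dose column gives a band, not a dose. At 80 mg/day or less, none of the three gives a target.

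**Step-up.** From 80 mg/day, reading across row 1 gives 160; moving down one row and reading across gives 320. The ratio is 320/160 = 2.

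**Escalation count.** Read literally, one step-up takes 80 mg/day (row 1 by current dose) to 320 mg/day (row 3). That is one increase but two rows, so it could meet the row-count wording and not the section 5.4 wording. Conversely, 1,440 to 1,920 is an increase, yet both doses sit in the last row by current dose.

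**Effect on one patient's denominator (illustration).** At 320 mg/day with three days left, the literal and regimen-column readings differ by 3 x (320 - 160) = 480 mg. Now assume step-down is triggered every day for five days, with the dose held at 160 once the regimen column runs out:

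- from 320: 5 x 320 = 1,600 against 320 + 4 x 160 = 960, ratio 1.67
- from 480: 5 x 480 = 2,400 against 480 + 320 + 3 x 160 = 1,280, ratio 1.88
- from 600: 5 x 600 = 3,000 against 600 + 480 + 320 + 2 x 160 = 1,720, ratio 1.74

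These are ratios of dose, not of the endpoint, because weight loss also depends on dose.

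**What rests on the SD.** The plan's power figure first: with 120 per arm, difference 0.1 and SD 0.25, power = Phi(0.1 / (0.25 x sqrt(2/120)) - 1.96) = Phi(3.10 - 1.96) = 87%, as stated. (A simulated Wilcoxon test gives 85%, close enough not to dispute the figure.) By the same formula, an SD of 0.30 gives about 73%, 0.35 about 60%, and 0.47 about 38%. The values 0.30 and 0.35 are assumptions, and 0.47 is the sponsor's own-center figure. If the difference were instead attenuated by an assumed 10%, 20% or 30% with SD 0.25, power would be 80%, 70% or 58%. The documents do not say how much of either change the grid wording would cause.

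**The case against.** The strongest reply is that the literal reading is not the intended one. The row states that its purpose is to lower intensity, and moving up the regimen column does so for seven of eight regimens. The literal reading also makes the 160 mg regimen in row 1 unreachable by any step-up. This stands: the text is ambiguous and incomplete, and a reader should not infer that step-down fails in practice.

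A reader might also infer that the primary denominator is distorted or the arm comparison biased. The documents do not show this. The denominator is the dose actually given. The grid is advisory, so nothing obliges a clinician to hold or raise a dose. It applies in both arms, and randomization is stratified by site, so site-level differences in reading should be roughly balanced and act mainly as noise. No share of patients above 5 L/24 h is given for either arm, and section 1.0 reports that a single SGLT2 inhibitor dose did not raise urine volume.

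Two limits apply to this reply. Balance by site does not cover a trigger that follows randomization and may respond to treatment: section 10.0 expects dapagliflozin to lower cumulative furosemide dose, and a step-down that leaves dose unchanged would block part of that. And advisory status does not restore the assumed uniformity, since discretion adds dose variation. No other section resolves the wording.

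**Conclusion.** The instruction table and the grid in section 5.3.2 contradict each other on the literal reading, and every alternative leaves doses without a defined step. That finding is exact and rests only on the printed table. It includes 80 mg/day, the start for loop-naive patients first dosed after enrollment, which has no step-down target under any reading.

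The consequences are risks. If sites or clinicians read the grid differently, dose variation grows, against the rationale for an SD of 0.25. If step-down leaves dose unchanged in strong responders, and these are more common on dapagliflozin, a true efficiency gain would be understated. Both conditions are assumptions, and neither effect can be sized from the documents. The worsening-heart-failure criterion inherits the ambiguity because its two wordings count different things.

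**What to change.** Reconcile the instruction table, the grid and the worsening-heart-failure criterion.

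- Replace the row moves with a table giving, for each current mg/day range, one explicit entry for output below goal and one for output above goal. It should cover the 80 mg/day start and regimens that are not in the grid's right column. The sponsor's clinicians choose the doses.
- Use one definition of the escalation count in the protocol summary, sections 2.2 and 5.4, and the SAP, stated so that it can be counted from the new table.

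The cost is rewording one table, its site card and one endpoint definition. No patients, visits or procedures are added.

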5.4 Clinical Event Committee

The CEC will consist of 3 independent clinicians, which will consist of at least one endocrinologist and at least one heart failure specialist. The members of this committee

will be independent of the study implementation teams and will be blinded to study arm assignment. This committee will review abstracted clinical data to determine when primary endpoints and major events have occurred. The CEC will review data for the following study outcomes:

- Potential inhospital worsening heart failure events identified by the following criteria:
 - New intravenous inotropic therapy
 - New admission to an intensive care unit
 - New non-invasive positive pressure ventilation with bilevel positive airway pressure
 - 2 or more increases in IV diuretic protocol intensity after Study Day 1
- 30-day readmission events for heart failure or diabetes-related care
- Prolonged hospitalization as a result of the following safety outcomes: hypotension requiring medical intervention or hypoglycemia requiring medical intervention
- In-hospital incidence of ketoacidosis
- Inpatient mortality for causality

All criteria and definitions will be pre-specified in detail in the Clinical Events Committee Charter. Only outcomes adjudicated as such by the Clinical Events Committee will be considered. If there are valid reasons for questioning an adjudication, such as an inexplicable outlier during analysis, the Principal Investigator may formally request a review of the case. In such situations, the Clinical Events Committee has final determination.

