Efficacy and Safety of Dapagliflozin in Acute Heart Failure

DICTATE-AHF

NCT 04298229

Protocol

A Randomized, Open-label Study of Dapagliflozin in Patients with or without Type 2 Diabetes Admitted with Acute Heart Failure

Principal Investigator:

[name] Director, HF and Transplant Section Vanderbilt Heart and Vascular Institute Vanderbilt University [name]

Co - Principal Investigator:

[name] Clinical Pharmacy Specialist Vanderbilt University [name]

Site Investigators:

[name]. – Vanderbilt University Medical Center [name]. - St Thomas Hospital System A. [name]. – Centennial Hospital [name] – University of Mississippi [name] – Integris Baptist Medical Center [name] – University of North Carolina

Clinical Coordinating Center:

[name]; [name]; [name]

Data Coordinating Center:

[name], [name], [name]

Sponsor:

Vanderbilt University Medical Center

PROTOCOL VERSION AND AMENDMENT TRACKING

Version Number/Amendment	Approval Date
1.4/ Original protocol	2.10.2020
2.0/Amendment One	1.4.2021
3.1/Amendment Two	6.14.2021
4.0/Amendment Three	9.21.2021

Abbreviations

Acute Decompensated Heart Failure			
B-type natriuretic peptide			
Blood pressure			
Clinical Coordinating Center			
Clinical Events Committee			
Data coordinating center			
Data and Safety Monitoring Board			
Emergency department			
Fractional excretion of sodium			
Heart failure with preserved ejection fraction			
Heart failure with reduced ejection fraction			
Intensive care unit			
Intravenous			
Left ventricular ejection fraction			
Principal Investigator			
Vanderbilt University Medical Center			
Worsening Heart Failure			

CLINICAL TRIAL SUMMARY

Title	A Randomized, Pilot Study of Dapagliflozin in Patients with or without Type 2 Diabetes Admitted with Acute Heart Failure
Study Objectives	The primary endpoint is to determine the cumulative change in weight (kilograms) per 40mg of IV furosemide equivalents from enrollment to day 5 or discharge (if earlier) between: 1) protocolized diuretic therapy and 2) dapagliflozin plus protocolized diuretic therapy guided by urine output.

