7.4 Reporting of Adverse Events and SAEs

All adverse events occurring from signing of the Informed Consent through the 30-day follow-up period will be collected and reported. The Site Investigator is responsible for monitoring the safety of patients enrolled into the study. The following adverse events are anticipated, disease related-events in patients with decompensated heart failure; however, they should still be reported on the Adverse Event form in the REDCAP Database (some may require reporting as study endpoints):

- New Ventricular Arrhythmia: Ventricular tachycardia lasting longer than 30 seconds, or frequent non-sustained VT causing hemodynamic instability with MAP < 60 mmHg requiring intervention or > 1 intra-cardiac defibrillation or external cardiac defibrillation shock or ventricular fibrillation requiring defibrillation or requiring transfer to the intensive care unit
- Hypotension: SBP < 90 for 2 repeated measurements within 30 minutes or lasting at least 30 minutes or symptomatic hypotension necessitating clinical intervention (defined as vasopressor support, intravenous fluid boluses, or initiation of inotropes)
 - Hypovolemic hypotension: subset of "hypotension" requiring fluid administration for hypovolemia
- *Cardiac arrest*: any ventricular arrhythmic or pulseless electrical event that requires immediate life-sustaining medical therapies
- Acute kidney injury requiring renal replacement therapy: an acute renal failure event that began during the study period and necessitates new renal replacement therapy during the hospitalization
- Prolonged hospitalization as a result of the following safety outcomes: hypotension requiring medical intervention or hypoglycemia requiring medical intervention
- Diabetic ketoacidosis as adjudicated by the CEC
- Death

All serious adverse events must be recorded in the Adverse Event Record of the patient's REDCAP database. All serious adverse events should be monitored until stabilization or resolution.

The process of reporting of SAEs will be as follows:

- 1. The investigator team informs the site investigator of an SAE
- 2. The site investigator reports the SAE to the local IRB and to the coordinating center and PI within 24 hours of being aware of the event. The site investigator will electronically submit the necessary supporting documentation to the coordinating site.
- 3. The coordinating center and PI will report the SAE to AstraZeneca.

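### Protocol 5.4 lets the Principal Investigator of an open-label trial send adjudicated cases back for review with no arm-masked selection rule, cut-off or record of the first decision

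*Protocol*

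**What the plan says.** The trial is open-label; Protocol 4.0 opens with "We will perform a randomized, open-label, multicenter trial".

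Protocol 5.4 sets up a three-member committee whose members "will be independent of the study implementation teams and will be blinded to study arm assignment". Its decisions fix the counts: "Only outcomes adjudicated as such by the Clinical Events Committee will be considered". The section then allows a second look. Given valid reasons to question an adjudication, "such as an inexplicable outlier during analysis, the Principal Investigator may formally request a review of the case". The next sentence settles who decides: "In such situations, the Clinical Events Committee has final determination".

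The outcomes listed for adjudication in 5.4 are in-hospital worsening heart failure, 30-day readmission for heart failure or diabetes, prolonged stay because of treated hypotension or hypoglycemia, ketoacidosis, and inpatient death (for its cause). Detail is left to a separate document: "All criteria and definitions will be pre-specified in detail in the Clinical Events Committee Charter". That Charter is not among the documents reviewed.

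The SAP analyses worsening heart failure and ketoacidosis as adjudicated by the CEC, and lists adjudicated readmission as its other secondary endpoint. It has no rule for events whose adjudication changes and no analysis on the decisions as first made.

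**The concern.** Blinding the committee protects each decision. It does not protect the choice of which cases get a second decision. Any second look overturns some fraction of first decisions. If cases are chosen by someone who knows the arm, more errors can be corrected in one arm than in the other, and the counts drift apart even though every vote was blind.

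The stated trigger does little to limit this. The adjudicated outcomes are analysed as yes/no or time-to-event. A single yes/no event is not a statistical outlier in any defined sense, so whether it is inexplicable depends on what the requester expected. The example also places the request in the analysis phase, when arm may be linked to outcome.

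At stake are both secondary endpoints and the adjudicated safety outcomes. In an open-label trial, blinded adjudication is the main protection these outcomes have.

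**Working it through.** **1. What the text controls at each step.**

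| Step | Control stated in the protocol or SAP |
|---|---|
| Who may ask | The Principal Investigator (Protocol 5.4) |
| Grounds | Valid reasons, with one example and no definition |
| Requester masked to arm | Not stated |
| Same selection rule for all cases | Not stated |
| Latest time for a request | Not stated; the example is during analysis |
| Who re-decides | Blinded CEC, with final say (5.4) |
| First decision kept and changes logged | Not stated |
| Analysis if decisions change | None in the SAP |

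The re-decision is controlled. The selection of cases is not.

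**2. Could the requester know the arm?** Neither document says that the Principal Investigator is masked. The trial is open-label, and under Protocol 7.4 site investigators report each SAE to the coordinating center and the Principal Investigator, after which "The coordinating center and PI will report the SAE to AstraZeneca". Knowledge of individual allocations is therefore plausible, but it is an inference.

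**3. Size, as a hypothetical.** The plan gives no figure on this point to reproduce, and no event, re-review or overturn rate. Taken from the plan: 120 per arm and two-sided alpha 0.05. Assumed: true event rate p in both arms; a fraction q of one arm's events removed and nothing changed in the other; two-proportion z-test.

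After removal the rates are p and p(1 − q). With SE = √{[p(1 − p) + p(1 − q)(1 − p(1 − q))]/120} and r = pq/SE, the rejection rate is about Φ(r − 1.96) + Φ(−r − 1.96).

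Worked case, p = 0.25:
- q = 0.10: 0.25 against 0.225. Odds ratio (0.225/0.775)/(0.25/0.75) = 0.87. SE = 0.0549, r = 0.025/0.0549 = 0.455. Rejection = Φ(−1.505) + Φ(−2.415) = 0.066 + 0.008 = 7.4%.
- q = 0.20: 0.25 against 0.20. Odds ratio (0.20/0.80)/(0.25/0.75) = 0.75. SE = 0.0538, r = 0.05/0.0538 = 0.929. Rejection = Φ(−1.031) + Φ(−2.889) = 0.151 + 0.002 = 15.3%.

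Over a range of event rates, summing exact binomial probabilities over all pairs of counts where |z| > 1.96:

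| Event rate p | q = 10% | q = 20% |
|---|---|---|
| 5% | 5.0% | 6.0% |
| 10% | 6.1% | 8.8% |
| 15% | 6.3% | 10.4% |
| 20% | 6.9% | 12.9% |
| 25% | 7.4% | 15.4% |
| 30% | 8.1% | 18.2% |

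**4. How many reversals does that take?** Starting from equal counts, the one-way removals in one arm needed for p < 0.05 are 6 of 6, 8 of 12, 10 of 18, 11 of 24 or 14 of 36. Three removals move the odds ratio from 1.00 to 0.73 at 12 of 120 (p = 0.49), or to 0.85 at 24 of 120 (p = 0.62). A few reversals shift the estimate but rarely produce significance alone.

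**The case against.** The strongest answer is the sentence that follows the clause: the committee has the final word, and it is independent and blinded. A reader of the clause alone might infer that the Principal Investigator can alter a count. The text rules that out. The safeguard stands, but it covers the decision and not the selection.

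A reader might also infer that the Principal Investigator is unblinded and asks after seeing results. The documents do not say so. Protocol 4.2 and 8.0 place analysis and data checks with the biostatistical team, and 8.0 describes data transfers at regular intervals with discrepancies queried. In that setting, analysis may mean ordinary data checking. What stands is that nothing in the text confines requests to that setting.

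The hypothetical is also demanding. At 25% events, 20% overturned means 6 of 30 in one arm. If a blinded committee reversed one re-reviewed case in four (an assumption), 24 of the 30 would have to be sent back, far more than a clause about odd cases suggests. Worsening heart failure rests largely on recorded facts such as inotrope use or ICU admission, which leaves less to overturn. The readmission endpoint is analysed by a stratified Cox model, so the two-proportion figures are only a rough proxy there.

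Finally, the Charter may already contain the missing rules. Protocol 5.4 assigns it criteria and definitions; whether it also governs re-review cannot be checked here.

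**Conclusion.** The point holds as a procedural gap, not as evidence of bias. In an open-label trial the plan names a route to re-adjudication and, in the protocol and SAP, leaves the selection of cases unmasked, without a cut-off and without a record of first decisions.

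Its reach is limited to worsening heart failure, 30-day heart failure or diabetes readmission, and adjudicated safety outcomes: ketoacidosis in the SAP, plus prolonged stay from hypotension or hypoglycemia in Protocol 2.4. A reader might infer that the main result is at risk, since 5.4 loosely says that the committee determines primary endpoints. The documents do not support this: the primary outcome in Protocol 2.1 is a measured weight change per loop-diuretic dose and is not on the adjudication list. Death is reviewed for cause, so the SAP's mortality count would not realistically move.

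Under the stated assumptions (120 per arm, no true effect, event rates of 5–30%, all reversals one way in one arm), the false-positive rate is about 5–8% with 10% of that arm's events overturned and about 6–18% with 20%. With reversals in both arms or in both directions, the effect would be smaller.

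**What to change.** Amend Protocol 5.4, or cite the Charter there if it already says this, so that:
- re-review requests are prepared without treatment arm, under one written rule applied alike to every case;
- requests close before adjudication is locked and merged with arm;
- each request is logged with its reason and with the first and the revised decision.

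Add to the SAP that, if any decision changes, the affected secondary and safety analyses are repeated on the decisions as first made and both results are reported.

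The cost is a few sentences, a log and at most one extra set of analyses. The drawback is slightly less freedom to correct an error found late. Genuine errors can still be corrected before the lock.
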